The results of all tested regression models will be presented in the technical appendix to the report, to show if the effect size and significance of the selected best model were sensitive to the choice of model.

Sample size calculation

No sample size was calculated for this study. The analysis is considered informative and will be carried out regardless of whether our study population is of a sufficient size to detect a statistically significant difference.

3. Limitations and sources of bias

Threats to validity

Internal validity

One of the main threats to the validity of this study is unobserved confounding. Unobserved confounding can occur at area, hospital, general practice or patient level. There is always a risk of unobserved confounding in non-randomised studies, but here the risk is larger due to the way patients have been selected for the ICTs, especially up to June 2017 when patients were primarily selected based on clinical judgement. This leads to potential selection bias. The majority of referrals come from GPs, though referrals are also received from other health care workers (e.g. community staff, mental health, social care).¹⁰ The lack of information on any non-clinical reasons for referring patients (for example, a close family member dying or moving away), together with a lack of primary care and community data, makes it difficult for us to identify what characteristics the referred patients were selected on and therefore to identify a matched control group that is similar to the intervention group in these characteristics. The uncertainty of the results due to potential unobserved confounding will not be reflected in the confidence intervals or p values, as these capture other kinds of uncertainties. Therefore, even a statistically significant result will need to be interpreted with caution. The IAU will perform some sensitivity analysis (see section on Sensitivity analysis, p. 31) to try to assess the presence of unobserved confounding.

If important predictive covariates are omitted from the matching and regression models, then unobserved differences between the groups may contribute to any or part of any difference in outcomes. These differences would in turn then erroneously be attributed to the intervention.

However, the risk of unobserved confounding at area or hospital level is mitigated by using local controls within NEHF.⁴⁹ Here, the local control group will use the same hospital services, thereby minimising the risk of bias due to differences between hospitals, for example the availability of EDOUs (see section on NEHF CCG, p. 8); differences in coding practices (that could bias the detection of comorbidities and therefore risk adjustment);^{50,51} or hospital changes as part of the local STPs that could impact on outcomes.

Furthermore, although matching will not ensure balanced groups on unobservable characteristics, it will ensure that the control and intervention groups within each locality are similar in observable variables to a reasonable degree. This is expected to produce a more similar control group than a non-matched comparison group.

There may be varying levels of engagement and interest in the ICTs among the health care professionals able to refer patients to the ICTs across the five localities. The decision to refer may therefore also be influenced by other factors such as primary care staff engagement or knowledge of the ICTs. As information on source of referral is not available, this cannot be accounted for in the analysis.

Some patients may have been offered a referral to an ICT but declined. If this is the case, this would introduce another selection mechanism to the treatment decision. No data are available.

If the regression model is mis-specified, this could lead to biased inferences. However, matching on key variables before running the regression decreases the dependency on the specification.

The IAU is assuming that patients in NEHF receiving care from ICTs access the other services available, such as other PACS interventions, in a similar manner to non-ICT patients in NEHF. This assumption will not hold if, for instance, ICT patients are referred to other services by the multidisciplinary team, in which case this could bias the results. However, NEHF CSU has confirmed that this is not expected to be the case.

The IAU uses the pre-period to determine hospital activity at baseline. However, patients in both the intervention and control groups may have received other services in that period, such as ER@H. If there is an imbalance between the groups who received such interventions, this would introduce a bias. However, there is no reason to believe that there should be a difference.

External validity

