- patients with a follow-up period of less than one month. This occurs when a patient dies within the same month of registering with a general practice within the CCG. A limitation of the derived data from the patient registration data available to the IAU is that it only allows us to determine the month within which a move or a death occurred (see section on Data derived from NHAIS, p.18). In these cases, both dates are set as the day of the extraction date on which the new address or death was recorded

- patients without a record of prior emergency or elective admission in the three-year pre-study period (defined in section on Pre-period, p.24). These will be excluded because prior hospital data are required to define baseline patient characteristics, in particular patient comorbidities
- patients referred to an ICT between mid-May and mid-June 2017.

The exclusion criterion relating to no prior admissions is likely to exclude some patients who were referred to the ICT. An analysis done by NEHF CCG found that 20% of patients referred to the ICTs by end of February 2017 had no admissions (emergency or elective) in the previous two years. By allowing a period of three years, it is hoped that the number of exclusions will be minimised, while not unduly identifying historic comorbidities that have since been resolved (see section on Pre-period, p. 24).

Patients who change general practice within the CCG will be considered to be assigned to the locality of the general practice at the start of the follow-up period. NEHF CCG has confirmed that there were only a few cases where patients who were referred to one ICT changed general practice and ICT team.

The intervention group will be identified using the pseudonymised list of patients referred to an ICT, supplied by NEHF CCG (see sections on Data from NEHF CCG (p. 19) and Exposure variable (p. 23). Patients referred to an ICT after the mid-May cut-off and before mid-June will be excluded from the intervention group as they will not have a follow-up period of at least one month. They will also be excluded from the potential control group, as they would have received the intervention within the study period. Any patients referred to ICTs after mid-June 2017 may be considered as potential controls for this study.

Sources of data

Secondary Uses Services national administrative data

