In summary, the NCDR will derive and provide the following limited data from the NHAIS database, for patients registered with a NEHF general practice at any time during the period mid-July 2015 to mid-June 2017:

- patients' month and year of birth
- patients' month and year of death
- patients' general practice code
- patients' extract date when the general practice code changed
- flag if a patient is resident in a nursing or residential care home in NEHF at any time during the period and the date of the move into the care home.

The dates of death and registering with a practice will be estimated by using the date of the extraction.

It is believed that data to mid-June 2017 (i.e. the June 2017 extract) will be of sufficiently good quality, but the IAU will do comparisons of monthly data to check this and adjust the study period accordingly. The data derived from NHAIS will be linked to the SUS data via a pseudonymised patient identifier.

Data from NEHF CCG

The IAU will request the following information from NEHF CCG:

- pseudonymised patient IDs for patients who were referred to ICTs from 27 July 2015 to mid-June 2017
- date of referral
- the locality of the ICT to which they were referred.

Information on patient IDs and date of referral will allow the IAU to identify the intervention group and the start dates of their intervention. Although only patients referred up to mid-May will be included in the intervention group, data on patients referred until mid-June will be needed to ensure that subsequent referrals are excluded from the control group. Patients referred to an ICT after mid-June 2017 can serve as a control patient for the study period of this evaluation. Information on locality for referred patients will allow the IAU to check that the general practice codes from NHAIS can be used to derive locality correctly. This will

confirm whether matching within localities and doing subgroup analyses by locality are feasible.

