Proportion of deaths in hospital will be used as a proxy for patients dying in their preferred place of death. While patients may not die in their preferred place outside of hospital, it is assumed for the purposes of this analysis that locations outside of hospital (e.g. home, care home, hospice) would always be preferred over dying in hospital. Proportion of deaths is calculated by combining information on hospital deaths from the SUS data with information on all deaths from the NHAIS data.

Delayed transfers of care will not be evaluated, as the IAU does not have access to reliable data.

Variable definitions

Bedding-in period and study period

The ICTs were launched on 27 July 2015 across all five NEHF localities. Although the ICTs developed their capacity and services at different rates across the five localities, they were running services immediately. This study will not include a bedding-in period (i.e. a period omitted from the analysis to allow time for the interventions to become established). Although the earliest start date for the intervention group is 27 July 2015, the study period will start in mid-July 2015 (the exact date being the date of the NHAIS monthly extraction) to allow for potential control patients to be included from that date.

The study period will end mid-June 2017 (the exact date being the date of the NHAIS monthly extraction). During this period, most of the patients referred to ICTs were selected based on clinical judgement.

Exposure variable

A person is considered to be in the intervention group (i.e. exposed to the intervention) if they were registered with a NEHF general practice and referred to an ICT between 27 July 2015 and mid-May 2017. By only including patients referred up to mid-May 2017, the IAU allows for at least one month of exposure to the intervention. Persons in the intervention group will be identified from the list of referred patients, supplied in pseudonymised form from NEHF CSU.

Index dates and follow-up period

Each patient will be followed up within the study period for a length of time specific to that patient. A patient's follow-up period will start from the index date, which is defined as:

- If the patient was referred to the ICT, then the date of their first referral. For the purpose of this analysis, this is the date at which they are considered to have started the intervention.

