- If the patient was not referred to the ICT (i.e. in the potential control group), then monthly potential index dates will be assigned, starting from the latest of the following:
 - the study period start date (see section on Bedding-in period and study period, p. 23)
 - date of earliest registration with a general practice in NEHF CCG, set as the date of the extraction in which they are first known to have been registered with a general practice in NEHF.

If a patient was referred more than once, only the first date is used, that is, if patients were discharged and then subsequently referred again, they are treated as though they stayed on the ICT register. No differentiation will be made between active or dormant patients (see section on Integrated care teams, p. 12).

For potential control patients, monthly index dates will be assigned from mid-July 2015 up to mid-May 2017. As the first and last monthly dates may be based on extraction dates (see

above and below), the dates set for all other months will for consistency also correspond to the extraction date of the corresponding month. This will also enable more accurate information on whether a patient was a care home resident at the index date, which is one of the potential covariates (see section on Baseline variables, p. 25).

A person's follow-up period ends when the person either dies, moves from NEHF CCG or the study period ends. Thus, the end date is defined as the earliest of the following dates:

- the end of the study period, that is mid-June 2017, set to the date of the last available NHAIS extract
- date of death, set to the date of the extraction in which death is first recorded
- date of de-registration from CCG general practice, set to the day before the date of the extraction in which they were first registered with a general practice outside NEHF.

A person's follow-up period may therefore be between approximately 1 and 23 months.

The date of death is estimated as the extraction date of when they were first recorded as having died. However, as the true death date could be as early as the day after the previous extraction date, there is a risk that the follow-up period is overestimated by up to a month, during which time the patient would have no recorded hospital activity. However, as it is unlikely that the day of the month that a person dies is other than random, this is unlikely to introduce bias between the intervention and control groups.

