One of the main threats to the validity of this study is unobserved confounding. That is, although the IAU anticipates that the intervention and matched control groups will be similar in terms of observed variables (such as age and prior number of hospital admissions), there may be systematic differences between these groups that we do not observe, for example characteristics that informed clinical judgement to refer to ICTs. There is always a risk of unobserved confounding in non-randomised studies, but here the risk is larger due to patients being selected for the ICTs primarily based on clinical input from GPs or other health professionals.¹⁰ The lack of information on the subjective reasons for referring patients, together with a lack of primary care and community data, makes it difficult for us to identify what characteristics the referred patients were selected on and therefore to identify a matched control group that is similar to the intervention group in these characteristics.

Although there is no definitive way to assess the effect of unobserved confounding, it is possible to compare the rates of the intervention and matched control groups on an endpoint unrelated to the intervention.⁴⁷ On the assumption that the intervention is unlikely to have had a large positive or negative impact on overall mortality within the follow-up period, then differences in mortality rates would make us doubt the performance of the matching. For example, if enrolled patients died at a higher rate than matched control patients, this might suggest that they were in worse health than controls at the point of enrolment.⁴⁸ However, there is also a possibility that good care may result in prolonged life and therefore less deaths during our follow-up period. The IAU will therefore compare the rates of all-cause mortality over the study period. The IAU will also perform a survival analysis using Kaplan-Meier estimates, censoring patients who moved or reached the end of the study period. Similar mortality and survival rates will be indicative of balanced groups, while differences would need to be interpreted with caution.

If there is found to be a difference in mortality between the intervention and control groups, the IAU will explore possible reasons for the imbalance and if possible consider subsetting the cohort in such a way as to remove any bias.

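### The under-one-month follow-up exclusion depends on death after the index date and acts differently in the ICT and control groups, in a direction the undefined month leaves open

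*Protocol*

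**What the plan says.** Under Definition of study cohort, the exclusions include "patients with a follow-up period of less than one month". The explanation attached is narrow: "This occurs when a patient dies within the same month of registering with a general practice within the CCG". Yet the same section counts the minimum from referral when it deals with late referrals, who "will be excluded from the intervention group as they will not have a follow-up period of at least one month".

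Under Index dates and follow-up period, the clocks start differently:
- ICT group: "If the patient was referred to the ICT, then the date of their first referral", which can be any day.
- Controls: the first and last monthly dates may be extract dates, and "the dates set for all other months will for consistency also correspond to the extraction date of the corresponding month".
- End of follow-up at death, both groups: "date of death, set to the date of the extraction in which death is first recorded".

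That section accepts that the rounding can overstate follow-up by up to a month and judges bias between the groups unlikely. The section on data derived from NHAIS places extracts on the first Sunday after the 13th and lists "month and year of death" among the supplied fields. Under Sensitivity analyses, mortality is the check on unobserved confounding: "The IAU will therefore compare the rates of all-cause mortality over the study period", with Kaplan-Meier curves alongside. The July 2018 addendum thins the index dates of younger controls but leaves the exclusion and the dating rules alone.

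**The concern.** A patient's recorded follow-up is known only after the index date, so a minimum length makes entry depend on surviving. Selection of this kind matters most when it differs between groups, and here the differing clocks make it differ. A control who dies the day after indexing is credited with a whole extract interval. An ICT patient who dies before the first extract after referral is credited only with what is left of the interval.

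The Background says that some ICT patients are near the end of life, and the Statistical analysis section notes that hospital use may rise in the last months. Early deaths are therefore informative records. Removing them distorts the mortality comparison meant to reveal whether referred patients were sicker than their controls. It also removes terminal admissions and places of death from the outcome results.

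**Working it through.** **Calendar.** First Sunday after the 13th, July 2015 to June 2017, gives 24 extracts from 19 July 2015 to 18 June 2017. That is 700 days in 23 intervals: 15 of 28 days and 8 of 35 (15 × 28 + 8 × 35 = 700). 700 / 30.44 = 23.0 months, which reproduces the protocol's upper limit of about 23 months.

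**Worked cases** (extracts on 16 August, 20 September and 18 October 2015):
- ICT patient referred 1 September, dies 10 September: end date 20 September, 19 days. Excluded under any reading of a month.
- ICT patient referred 1 September, dies 25 September: end date 18 October, 47 days. Kept. Losses among ICT patients are mainly deaths before the first extract after referral.
- Control indexed 16 August, dies 17 August: end date 20 September, 35 days. Kept under any reading.
- Control indexed 20 September, dies 21 September: end date 18 October, 28 days. Kept if a month is 28 days, excluded if it is 30 or 31.

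**Share of 30-day deaths lost.** Counted day by day with constant mortality, a 28-day month loses about 42% of ICT and 0% of control deaths in the first 30 days. With 30 days it loses about 48% of ICT deaths. For controls, only those indexed before a 28-day gap are affected: 15/23 × 28/30 = 61%.

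**Effect on the mortality rate ratio.** Assumptions: ICT referrals spread evenly from 27 July 2015 to 14 May 2017; control index dates spread evenly over the 23 eligible extracts; identical true mortality in both groups. The protocol gives no mortality rate, so the rates below are assumed. The ratio is retained deaths over recorded person-time, ICT against control. Person-time barely moves, so it is close to (1 − ICT share lost) / (1 − control share lost).

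| Assumed monthly mortality | One month read as | ICT deaths lost | Control deaths lost | Ratio when truth is 1 |
|---|---|---|---|---|
| 2% throughout | 28 days | 3.9% | 0% | 0.961/1 = 0.96 |
| 2% throughout | calendar month | 4.6% | 5.4% | 0.954/0.946 = 1.01 |
| 2% throughout | 30 days | 4.5% | 5.8% | 0.955/0.942 = 1.01 |
| 2% throughout | 31 days | 4.8% | 5.8% | 0.952/0.942 = 1.01 |
| 4% in first month, then 2% | 28 days | 7.3% | 0% | 0.927/1 = 0.93 |
| 8% in first month, then 2% | 28 days | 12.9% | 0% | 0.871/1 = 0.87 |
| 8% in first month, then 2% | calendar month | 15.2% | 17.5% | 0.848/0.825 = 1.03 |
| 8% in first month, then 2% | 30 days | 14.8% | 18.8% | 0.852/0.812 = 1.05 |

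**In patients.** At 2% a month and a 28-day reading, 0.82% of ICT patients are dropped: 900 × 0.0082 ≈ 7. At 8% in the first month it is 3.3%, or about 30.

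**Without the exclusion.** With the same rounding of deaths but nobody dropped, the ratio is 1.00 in every mortality scenario above. When true mortality is equal, the distortion comes from the exclusion and not from the rounding alone.

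**The case against.** The strongest reply is that a reader might infer a one-sided flaw: early ICT deaths dropped, early control deaths kept, ICT mortality always understated. The protocol does not support that. It never defines a month in days. On a 30-day, 31-day or calendar-month reading controls lose slightly more early deaths, and the small bias runs the other way. Its own usage does not settle the matter: mid-May to mid-June 2017 is 14 May to 18 June, 35 days, which meets any definition, and 700 days is 23 calendar months as well as 23 intervals.

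Second, the attached explanation could mean that only people who register and die within one extract month are excluded. A long-registered ICT patient who died soon after referral would then stay in. That reading is possible, but it fits neither the general wording of the exclusion nor the minimum counted from referral in the same section. The passages need reconciling.

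Third, the effect is modest against sampling error. At 2% a month there are about 188 deaths per group of 900, so the standard error of the log ratio is about √(2/188) = 0.10, and ln 0.96 = −0.04 is under half of that. This stands. The 0.87 rests on an assumed 8% first-month mortality, and no hospital-use outcome was simulated.

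Fourth, the rounding of death dates is disclosed, and the Statistical analysis section promises to compare follow-up length and reasons for leaving. The disclosure stands, so the rounding is secondary. That comparison, however, would describe patients in the study and not those already removed by the exclusion.

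**Conclusion.** The point holds as a selection problem of uncertain direction. As worded, the exclusion conditions on survival after the index date, and the two groups meet it differently because one clock starts on a true date and the other on an extract date. Neither the statement that bias is unlikely nor the addendum considers this.

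Under the assumed mortality patterns, a null mortality ratio reads between 0.87 and 0.96 if a month is 28 days, and between about 1.01 and 1.05 if it is 30 or 31 days. The protocol supplies neither the definition nor the early mortality needed to choose among these. A reader should not conclude that ICT mortality is necessarily understated, or that the rounding of death dates alone biases the comparison. What is established is that some early deaths are removed from the mortality and survival check, and with them terminal hospital use and places of death, by a rule that treats the groups unequally and that the design does not need.

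**What to change.** 1. Apply the one-month minimum only to the index date relative to study end: index date in mid-May 2017 or earlier, in both groups.
2. Exclude nobody for death or a move after the index date. The planned offset for days in the study already handles short follow-up.
3. Reword the explanation so that it matches the rule. People whose registration and death first appear in the same extract have no time at risk and can be covered by a separate condition of being alive and registered at the index date.
4. Report, by group, the number of deaths before the first extract after the index date.
5. Optionally, as a sensitivity analysis, date in-hospital deaths from SUS and place the others using the supplied month of death.

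No new data are needed, and the first two changes remove the selection whichever definition of a month was meant. The costs are that a few very short follow-up records enter the models and, since the addendum shows that matching and analysis have been run, that the matching against about 750,000 control records and the outcome models would have to be repeated.
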